3.2 Analysis Populations

3.2.1 *Safety Set*

The Safety Set (SS) consists of all patients who receive at least 1 dose of study drug (NM21-1480). Unless otherwise specified, the SS will be the default analysis set used for all analyses.

3.2.2 *Efficacy Analysis Set*

The Efficacy Analysis Set (EAS) consists of all patients who received at least one dose of study drug (NM21-1480) and have measurable baseline disease. The Efficacy Analysis Set will be the primary analysis set for efficacy.

. The final analysis will not be performed before all patients have either reached the first post-baseline tumor assessment or discontinued clinical response evaluation.

3.2.3 *Dose-Determining Set*

The dose-determining set includes all Safety Run-in patients from the SS of Part A who either completed the minimum exposure requirement and have sufficient safety evaluations or experienced a DLT. Patients will be considered to have met the minimum exposure requirement if they received at least 80% of either originally-assigned dose within the first cycle of dosing

(i.e., 80% of either the dose administered for Cycle 1/Day 1 [C1D1] or Cycle 1/Day 15 [C1D15]). The length of the DLT evaluation period is 28 days.

Patients who do not experience a DLT during the first cycle will be considered to have sufficient safety evaluations if they have been observed for ≥ 28 days following the first dose and are considered by both the Sponsor and Investigators to have enough safety data to conclude that a DLT did not occur.

3.2.4 *Pharmacokinetic Set*

The PK set will consist of all patients who receive at least 1 dose of NM21-1480 and have at least 1 post-dose PK blood collection with associated bioanalytical results. The PK set will be used for summaries and listings of PK data.

3.3 Subject Data and Study Conduct

Unless specified otherwise, analyses for Part A will be presented by dose level and in total, analysis for Part A-2 will be presented in total, and analysis for Part B will be presented by cohort and in total. Additionally, a total for all patients across Part A and Part A-2 will be presented, as will a total for all Part B patients who received NM21-1480, and a total for all patients in any part who received NM21-1480 at the 800 mg dose level.

3.3.1 *Subject Disposition*

Counts and percentages of subjects who were pre-screened and screened (signed informed consent for pre-screening and main study, respectively), failure screening, and enrolled in the study will be summarized with denominator based on all screened subjects. Reasons for screen failure will be summarized.

Counts and percentages of patients who discontinued from the study treatment, and who completed or discontinued from the study will be summarized with denominator based on all enrolled patients. Reasons for treatment discontinuation and for study discontinuation will be summarized.

All disposition data will be listed by patient.

3.3.2 *Protocol Deviations*

Counts and percentages of patients with protocol deviations by deviation category will be summarized for all enrolled patients. All CSR reportable protocol deviations will be listed.

3.3.3 *Analysis Populations*

Counts and percentages of subjects in each analysis population will be summarized with denominator based on all enrolled patients.

3.3.4 *Demographic and Baseline Characteristics*

The following demographic and baseline characteristics will be summarized:

- Age (years) and age categories (<65 years, ≥ 65 years)
- Sex
- Childbearing potential
- Race
- Ethnicity

- Height (cm)
- Weight (kg)
- Body mass index (BMI) (kg/m²) and BMI categories (<30 kg/m², ≥30 kg/m²)

Demographic and baseline characteristics will be summarized with descriptive statistics or counts and percentages of subjects as appropriate for patients in the safety set, efficacy analysis set, and pharmacokinetic set. If two sets are identical, only one version of the table will be presented.

All demographics and baseline characteristics will be listed by patient.

3.3.5 *Cancer History*

The primary cancer type/diagnosis, stage at initial diagnosis, histological/cytological diagnosis, grade, stage at study entry, time from initial diagnosis until informed consent, time from last progression until informed consent, PD-L1 status, MSI-H status (Cohort B8), d-MMR status (Cohort B8), Oncotype Dx Score, and Tumor Mutational Burden (TMB) will be summarized. For time from initial diagnosis and time from last progression, if the day of diagnosis/progression is missing, the day will be imputed as the 15th of the month, and if the month of diagnosis/progression is missing, the month and day will be imputed as July 1 for the purpose of the duration computation.

The number of patients who have mutations vs wild type will be summarized along with the assessment method for the following mutations: BCRA1, KRAS, EGFR, ALK, ROS1, BRAF, HER2, AKT1, MEK1, NRAS, PIK3A, RET, STK11, PTEN, and NTRK.

Patients' prior anti-cancer treatment will be summarized, to include the number of prior lines of therapy, the treatment setting (adjuvant, maintenance, etc), the best response to the most recent prior regimen, and the numbers of patients who received prior checkpoint inhibitors, radiotherapy, and cancer surgery will be summarized. The number of patients who had any irAEs and grade ≥3 irAEs during prior anti-cancer therapy will be summarized.

All primary cancer history, mutation assessment, prior cancer therapy, radiotherapy and surgery, and all irAEs during prior cancer therapy will be listed by patient.

3.3.6 *Medical History*

Medical history will be coded to system organ class and preferred term using the Medical Dictionary for Regulatory Activities (MedDRA) version 25.0. All medical history will be listed by patient.

3.3.7 *Concomitant Medications and Procedures*

Concomitant medications will be coded to anatomical therapeutic chemical (ATC) class and preferred term using the WHO Drug Dictionary (WHODrug Global B3, Version March 2022). Medications or procedures will be considered prior medications/procedures if they stopped prior to the first dose of study drug and concomitant medications/procedures if they were taken at any time after the first dose of study drug (i.e., started prior to the first dose of study drug and were ongoing or started after the first dose of study drug).

If a medication or procedure has incomplete start or stop dates, dates will be imputed to determine whether a medication/procedure should be considered prior or concomitant. If a medication/procedure start date is incomplete, the first day of the month will be imputed for

missing day and January will be imputed for missing month. If a medication/procedure stop date is incomplete, the last day of the month will be imputed for missing day and December will be imputed for missing month. Incomplete start and stop dates will be listed as collected without imputation.

All prior and concomitant medications and procedures will be listed by patient.

3.3.8 Study Drug Exposure and Compliance

The number of patients who received NM21-1480 at each planned time point (Cycle 1 Day 1, Cycle 1 Day 15, Cycle 2 Day 1, etc.) as well as the total number of NM21-1480 infusions per patient will be summarized. The number of patients with infusion interruptions will be summarized, along with the reason for interruption, and duration of interruptions. The planned and total infusion volume will be summarized, as will the total dose administered (mg). The number of patients whose IV rate was reduced will be summarized, along with the reason for rate reduction. Summaries of exposure will be presented for both the Safety Set and the Efficacy Analysis Set. If the two sets are identical, only one version will be presented.

The planned and actual dose administered (mg) will be summarized. The number of patients whose infusion was interrupted or who did not receive all volume will be summarized along with the reason.

All NM21-1480 administration data will be listed by patient.

3.4 Efficacy Assessment

Efficacy data will be summarized based on the Efficacy Analysis Set. The final analysis will not be performed before all patients have either reached the first post-baseline tumor assessment or discontinued clinical response evaluation.

Unless specified otherwise, analyses for Part A will be presented by dose level and in total, analysis for Part A-2 will be presented in total, and analysis for Part B will be presented by cohort and in total.

For any parameters involving RECIST v1.1 or iRECIST response assessments, the assessment date will be based on the date of the imaging scans rather than the date of the clinical evaluation. In the event that an evaluation is made based on scans coming from multiple days, the earliest scan date will be used for PD, iUPD, and CPD assessments and the latest scan date will be used for CR, iCR, PR, iPR, SD, iSD, and NE assessments.

3.4.1 Definition of Efficacy Endpoints

3.4.1.1 Best Overall Response (BOR)

Only tumor assessments performed before the start of any subsequent anticancer therapies and no later than 30 days after last dose will be considered in the assessment of BOR. Clinical deterioration or clinical progression noted on the end of treatment or end of study eCRFs will not be considered as documented progressive disease. BOR will be derived overall, and by 6 weeks, by 9 weeks, by 12 weeks, and by 15 weeks following the start of study treatment. As the Week 6 and Week 12 tumor response assessments have protocol-specified windows of day 39-43 and day 79-85 respectively, assessments on day 43 (6 weeks + 1 day) and day 85 (12 weeks + 1 day) will be counted toward BOR for their respective weeks. BOR will be derived for the following combinations of conditions:

- Based on investigator RECIST v1.1 assessment, requiring CR/PR confirmation,
- Based on investigator RECIST v1.1 assessment, without CR/PR confirmation,
- Based on central RECIST v1.1 assessment, requiring CR/PR confirmation (part B only),
- Based on central RECIST v1.1 assessment, without CR/PR confirmation (part B only),
- Based on investigator iRECIST assessment, requiring iCR/iPR confirmation (part B only),
- Based on investigator iRECIST assessment, without iCR/iPR confirmation (part B only),
- Based on central iRECIST assessment, requiring iCR/iPR confirmation (part B only),
- Based on central iRECIST assessment, without iCR/iPR confirmation (part B only).

Precedence for best overall response according to RECIST v1.1 is determined as follows, in descending order:

- CR – When confirmation of CR is required, at least 2 assessments of CR at least 4 weeks apart and before any progressive disease (PD). If CR is not confirmed by a subsequent CR, then for the purpose of BOR determination it will instead be considered SD if it fell ≥ 39 days after the start of treatment or NE if it fell < 39 days weeks after start of treatment. When confirmation of CR is not required, at least 1 assessment of CR before any progressive disease (PD).
- PR – When confirmation of PR is required, at least 2 assessments of PR or better at least 4 weeks apart weeks apart any before any progressive disease (PD). If an initial PR is followed by a CR assessment ≥ 4 weeks later, then the PR is considered confirmed. If PR is not confirmed by a subsequent PR or CR, then for the purpose of BOR determination it will instead be considered SD if it fell ≥ 39 days after the start of treatment or NE if it fell < 39 days weeks after start of treatment. If an initial CR is followed by a PR assessment, the PR assessment would generally be considered as PD due to the (re)appearance of new lesions following CR. When confirmation of PR is not required, at least 1 assessment of PR before any progressive disease (PD).
- SD (applicable only to patient with measurable disease at baseline) – At least 1 stable disease assessment (or better) ≥ 39 days after start of treatment and before any progressive disease (PD). For the version of best overall response requiring confirmation for CR/PR, an unconfirmed CR or PR will generally be considered as SD as long as it occurs ≥ 39 days after start of treatment.
- PD – Progressive disease ≤ 12 weeks after first dose of study drug (and not qualifying for CR, PR, or stable disease). PD assessments on Day 85 will be counted as falling within 12 weeks, as the protocol-specified window for the Week 12 tumor response assessment is 79-85 days.
- Not Evaluable – All other cases (i.e., not qualifying for CR or PR and without stable disease after at least 39 days or early progression within the first 12 weeks).

Precedence for best overall response according to iRECIST is determined as follows:

- iCR – When confirmation of iCR is required, at least 2 assessments of iCR at least 4 weeks apart before any confirmed progressive disease (iCPD). If iCR is not confirmed by a subsequent iCR, then for the purpose of BOR determination it will instead be considered iSD if it fell ≥ 39 days after the start of treatment or NE if it fell < 39 days weeks after start of treatment. When confirmation of iCR is not required, at least 1 assessment of iCR before any confirmed progressive disease (iCPD).

- iPR – When confirmation of iPR is required, at least 2 assessments of iPR or better at least 4 weeks apart weeks apart before any confirmed progressive disease (iCPD). If an initial iPR is followed by an iCR assessment \geq 4 weeks later, then the iPR is considered confirmed. If iPR is not confirmed by a subsequent iPR or iCR, then for the purpose of BOR determination it will instead be considered iSD if it fell \geq 39 days after the start of treatment or NE if it fell $<$ 39 days weeks after start of treatment. If an initial iCR is followed by an iPR assessment, this would generally be considered as progressive disease (iUPD or iCPD) due to the reappearance of new lesions following iCR. When confirmation of iPR is not required, at least 1 assessment of iPR before any confirmed progressive disease (iCPD).
- SD (applicable only to patient with measurable disease at baseline) – At least 1 stable disease assessment (or better) \geq 39 days after start of treatment and before any confirmed progressive disease (iCPD). For the version of best overall response requiring confirmation for iCR/iPR, an unconfirmed iCR or iPR will generally be considered as iSD as long as it occurs \geq 39 days weeks after start of treatment.
- iUPD – Unconfirmed progressive disease \leq 12 weeks after first dose of study drug (and not qualifying for iCR, iPR, or iSD). iUPD assessments on Day 85 will be counted as falling within 12 weeks, as the protocol-specified window for the Week 12 tumor response assessment is 79-85 days. If iUPD is followed by only NE and/or iUPD assessments then it will be considered iUPD for the purpose of best overall determination. If an iUPD assessment is followed by an iCPD assessment, then it will be considered iCPD for the purpose of best overall response determination.
- iCPD – Confirmed progressive disease \leq 12 weeks after first dose of study drug (and not qualifying for iCR, iPR, or iSD). iCPD assessments at the nominal “Week 12” visit will be counted, even if are more than 12 weeks after the first dose of study drug based on date. If the first response assessment is iUPD that is later confirmed by an iCPD assessment, then the best overall assessment will be considered to be iCPD.
- Not Evaluable – All other cases (i.e., not qualifying for iCR or iPR and without iSD after at least 39 days or early progression within the first 12 weeks).

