In Part A, NM21-1480 (dose levels 1 through 7 in the escalation phase) will be administered as a single IV infusion every 14 days for a total of 2 infusions per treatment cycle (4 weeks). Each treatment cycle comprises 2 doses of study drug administered on Days 1 and 15. Treatment for the second cycle is administered on Days 29 and 43, with a response assessment between Days 52 and 56 after the first dose of every other treatment cycle in Part A (i.e., every 8 weeks at the “8-Week Assessment”, see [Table 7-1](#) for details). In Part A, response assessment between Days 52 and 56 and between Days 108 and 112, respectively, is conducted for all patients still in the study, independent of the number of study drug administrations received during the previous 8-week/2-treatment cycles. Following each treatment cycle, the decision to treat a patient with additional cycles of NM21-1480 will be based on tolerability of the study drug and tumor response evaluation performed every 8 weeks i.e., in the week prior to administration of NM21-1480 in all odd number treatment cycles (e.g., Cycles 3, 5, 7, etc.). For optional Part A-2 and Part B, depending on SMC decision on dose levels and dosing intervals to be chosen for this expansion cohort phase, treatment cycles and dosing intervals may remain the same as described above for Part A (i.e., dosing intervals of approximately 14 days). In Part B of the study, NM21-1480 will thus be administered as a single IV infusion approximately every 14 days at the 800mg flat dose, based on Part A PK data which do not indicate substantial accumulation over time with this dosing interval; the 800mg dose of NM21-1480 thus represents presumptive RP2D to be further studied in Part B. Optional Part A-2 of the study will explore one more higher dose level (1400mg flat dose with approximately 14-day dosing interval) than was studied in Part A. Such 1400mg dose level will be explored applying strict stopping criteria and respecting a 28-day DLT evaluation period before more than 6 subjects are exposed. PK data for this 1400mg dose level in Part A-2 will be closely followed and in case of observation of relevant drug accumulation over time, the dosing interval for this dose may be adjusted to approximately every 21 days, resulting in treatment cycles of 6 weeks in such case. In optional Part A-2 and Part B of the study, response assessment is done every 6 weeks for the first 24 weeks patients are on active treatment, before switching to a response assessment every 8 weeks thereafter. Following each response assessment in optional Part A-2 and Part B, the decision to treat a patient with additional dose administrations of NM21-1480 will be based on tolerability of the study drug, perceived clinical benefit and tumor response evaluation performed every 6 weeks (first 24 weeks) or 8

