7.1.6 Schedule of Assessments

Table 7-1 Schedule of Assessments (2-week Dosing Interval; APPLIES TO ALL PARTS [A, A-2 AND B] OF THE STUDY)

Period	Screening Period*		Treatment Period ^d (2-week Dosing Interval/4-Week Treatment Cycles)				Follow-up Period ^a	Survival Follow-up ^b
Visit Name	Pre-Screen (Cohorts B2, B3, B5 and B8 only) ^{bb,dd,ee}	Screening	Cycle Day 1 Treatment Visit ^e	Cycle Day 15 Treatment Visit ^e	Cycle 1 Day 21±3 ^{gg} (Biopsy Visit)	Imaging and Treatment Response Assessment Visits ^c	Follow-up (FU) 1, FU2, and FU3 Visits	
Time point (Day / Week)	Day -42 to -29	Day -28 to -1	C1: Day 1 / Week 1 C2: Day 29±2 / Week 5 C3: Day 57±3 / Week 9 C4: Day 85±3 / Week 13 C5: Day 113±3 / Week 17 C6: Day 141±3 / Week 21 C7: Day 169±3 / Week 25 C8: Day 197±3 / Week 29	C1: Day 15±2 / Week 3 C2: Day 43±2 / Week 7 C3: Day 71±3 / Week 11 C4: Day 99±3 / Week 15 C5: Day 127±3 / Week 19 C6: Day 155±3 / Week 23 C7: Day 183±3 / Week 27 C8: Day 211±3 / Week 31 ^e		Day 39-43 / Week 6 (Pt A-2 and B only) Day 52-56 / Week 8 (Pt A only) Day 79-85 / Week 12 (Pt A-2 and B only) Day 108-112 / Week 16 (Pt A only) Day 120-127 / Week 18 (Pt A-2 and B only) Day 164-168 / Week 24 (Pts A, A-2 and B) Day 220-224 / Week 32 (Pts A, A-2 and B) ^c	FU1: 0 to 30 days post discontinuation FU2: 60 days ± 7 post discontinuation FU3: 90 days ± 7 post discontinuation	Every 3 months ± 7 days
ICF/HIPAA ^f	x ^{bb}	x						
Eligibility Criteria		x						
Demographics & medical history ^{g,h}		x						
Diagnosis & confirmation stage		x						
Tumor-specific therapy history ^{ff}		x						
Hepatitis B and C, & HIV testing ⁱ		x						
CD4 T-cell count ^l		x						
Covid-19 vaccination confirmation or negative Covid-19 polymerase chain reaction (PCR) test		x						
NM21-1480 infusion ^g			x	x				
Vital signs ^k		x	x	x			x	
Height		x						
Weight		x	x (Odd-numbered cycles only)				x (FU1 only)	
Physical exam ^l		x	x	x			x	
Oxygen saturation ^m			x	x				
ECOG performance		x	x	x			x	

Period	Screening Period*		Treatment Period ^d (2-week Dosing Interval/4-Week Treatment Cycles)				Follow-up Period ^a	Survival Follow-up ^b
Visit Name	Pre-Screen (Cohorts B2, B3, B5 and B8 only) ^{bb,dd,ee}	Screening	Cycle Day 1 Treatment Visit ^c	Cycle Day 15 Treatment Visit ^c	Cycle 1 Day 21±3 ^{gg} (Biopsy Visit)	Imaging and Treatment Response Assessment Visits ^c	Follow-up (FU) 1, FU2, and FU3 Visits	

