3 STATISTICAL METHODOLOGY

3.1 General Considerations

3.1.1 *Analysis Groupings*

Unless specified otherwise, analyses for Part A will be presented by dose level and in total, analysis for Part A-2 will be presented in total, and analysis for Part B will be presented by cohort and in total. Additionally, for the analysis of demographic, safety, PK, and immunogenicity data, a total for all patients across Part A and Part A-2 will be presented, as will a total for all Part B patients who received NM21-1480, and a total for all patients in any part who received NM21-1480 at the 800 mg dose level.

3.1.2 *Analysis Day*

Analysis day will be calculated from the date of first dose of study treatment. The day of the first dose of study drug will be Day 1, and the day immediately before Day 1 will be Day -1. There will be no Day 0.

3.1.3 *Definition of Baseline*

Baseline is defined as the last measurement prior to the start of study treatment.

3.1.4 *Summary Statistics*

Categorical data will generally be summarized with counts and percentages of subjects. The denominator used for the percentage calculation will be clearly defined. Continuous data will generally be summarized with descriptive statistics including n (number of non-missing values), mean, median, standard deviation, minimum, and maximum.

3.1.5 *Hypothesis Testing*

No hypothesis testing will be provided.

3.1.6 *Evaluation of Site Effect*

Site effect will not be analyzed.

3.1.7 *Handling of Missing Data*

Unrecorded data values will be recorded as missing. Only recorded (i.e. complete) data values will be used for statistical analyses. In general, invalid or missing values will not be imputed unless stated otherwise.

- For BOR and ORR, patients in the Efficacy Analysis Set who do not have sufficient on-study tumor assessments to characterize response will be included in the denominator when calculating BOR percent and ORR, and will thus be treated as non-responders. Further details are found in section [3.4.1.1](#).
- In cases of missing or incomplete dates (e.g. AEs and concomitant medications or procedures), the missing component(s) will be assumed as the most conservative value possible. For the detailed missing/partial data handling conventions for treatment-emergent adverse events see Table 2 in Appendix A. The actual data values as they appear in the original case report forms (CRFs) will be presented in the data listings.

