3.4.1.2 Objective Response Rate (ORR)

Objective response rate according to RECIST v1.1 (or iRECIST for Part B only) is defined as the percentage of patients with a best overall response of CR or PR (or iCR or iPR) out of all patients in the efficacy analysis set for the given group (dose level, cohort, or arm).

Overall ORR and ORR by 6 weeks, by 9 weeks, by 12 weeks, and by 15 weeks post start of study treatment will be derived. As the Week 6 and Week 12 tumor response assessments have protocol-specified windows of day 39-43 and day 79-85 respectively, assessments on day 43 (6 weeks + 1 day) and day 85 (12 weeks + 1 day) will be counted toward ORR for their respective weeks. ORR will be derived for the following combinations of conditions:

- Based on investigator RECIST v1.1 assessment, requiring CR/PR confirmation,
- Based on investigator RECIST v1.1 assessment, without CR/PR confirmation,
- Based on central RECIST v1.1 assessment, requiring CR/PR confirmation (part B only),
- Based on central RECIST v1.1 assessment, without CR/PR confirmation (part B only),
- Based on investigator iRECIST assessment, requiring iCR/iPR confirmation (part B only),
- Based on investigator iRECIST assessment, without iCR/iPR confirmation (part B only),

- Based on central iRECIST assessment, requiring iCR/iPR confirmation (part B only),
- Based on central iRECIST assessment, without iCR/iPR confirmation (part B only).

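### The SAP's 6-, 9-, 12- and 15-week response landmarks do not fit the Part A scan schedule: the 6-week row holds no scheduled scan, the protocol's 16-week landmark is dropped, and SAP section 6 does not record the change

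*SAP*

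**What the plan says.** **SAP.** Section 3.4.1.1: "BOR will be derived overall, and by 6 weeks, by 9 weeks, by 12 weeks, and by 15 weeks". Section 3.4.1.2: "Overall ORR and ORR by 6 weeks, by 9 weeks, by 12 weeks, and by 15 weeks post start of study treatment". Neither is limited by part, although the same sections mark the central-read and iRECIST versions as Part B only. Section 3.4 presents Part A efficacy by dose level and in total, and 3.4.2.1 and 3.4.2.2 put the landmark rows in one table for each dose level, cohort or arm. The Day 43 and Day 85 limits are justified by "protocol-specified windows of day 39-43 and day 79-85 respectively". Under 3.1.7, patients in the Efficacy Analysis Set without enough assessments "will be included in the denominator when calculating BOR percent and ORR, and will thus be treated as non-responders".

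**Protocol.** Table 7-1 labels those two windows "Day 39-43 / Week 6 (Pt A-2 and B only") and "Day 79-85 / Week 12 (Pt A-2 and B only"). For Part A, section 7.1 sets "response assessment between Days 52 and 56 and between Days 108 and 112", and Table 7-1 agrees ("Day 108-112 / Week 16 (Pt A only")). The Synopsis (Efficacy Analyses) and 10.6.2 both ask for Part A tabulations overall and at 8 and 16 weeks, tied to the imaging frequency. For Part A-2 they disagree: the Synopsis gives 6 and 12 weeks, 10.6.2 gives 8 and 16.

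**SAP section 6** lists limited enrolment, unopened cohorts and the absence of interim analyses. It does not mention landmarks.

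**The concern.** The SAP applies one set of landmarks, built on the Part A-2 and Part B scan calendar, to a part scanned every 8 weeks. A landmark that closes before the first scheduled scan yields a response rate of zero that reflects the calendar rather than the drug. A landmark that closes just before the second scan leaves that scan out. At stake is how the Part A landmark rows are read. One of them is an artefact, one of the two time points the protocol specifies is missing, and the section meant to record departures from the protocol says nothing about it.

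**Working it through.** **Inputs**

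- Part A scan windows: Week 8 = Days 52-56, Week 16 = Days 108-112 (protocol 7.1 and Table 7-1).
- SAP landmarks: 6, 9, 12 and 15 weeks (SAP 3.4.1.1, 3.4.1.2).
- Confirmation: two assessments at least 4 weeks (28 days) apart (protocol 10.6.2.2; SAP 3.4.1.1).
- 26 patients exposed in Part A (protocol 5.3.2). Measurable disease is an entry criterion (7.2.1, criterion 8), so 26 is taken as the denominator, with 25 as the alternative.
- One colorectal patient had an unconfirmed partial response at week 16 and had progressed by week 24 (protocol 5.2).

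**The SAP's own limits reproduce.** 6 × 7 + 1 = Day 43 and 12 × 7 + 1 = Day 85. On the same count, 9 weeks = 9 × 7 = Day 63 and 15 weeks = 15 × 7 = Day 105. The protocol's landmarks are 8 × 7 = Day 56 and 16 × 7 = Day 112.

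**Scheduled Part A scans inside each limit**

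| Landmark | Limit | Scheduled scans included |
|---|---|---|
| 6 weeks (SAP) | Day 43 | none |
| 9 weeks (SAP) | Day 63 | Week 8 |
| 12 weeks (SAP) | Day 85 | Week 8 |
| 15 weeks (SAP) | Day 105 | Week 8 |
| 8 weeks (protocol) | Day 56 | Week 8 |
| 16 weeks (protocol) | Day 112 | Weeks 8 and 16 |

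Week 16 opens 108 − 105 = 3 days after the 15-week limit and closes 112 − 105 = 7 days after it. A one-day allowance at 9 and 15 weeks (Days 64 and 106) changes nothing.

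**The 6-week row.** With no scan and every patient in the denominator, ORR is 0/26. The exact upper limit is 1 − 0.025^(1/26) = 13.2%. For 0/25 it is 1 − 0.025^(1/25) = 13.7%.

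**The missing 16-week row.** Week 8 and Week 16 scans lie between 108 − 56 = 52 and 112 − 52 = 60 days apart, which is more than 28. A partial response at Week 8 would therefore have been confirmed by the one at Week 16. Since the response is described as unconfirmed, and the patient had progressed by week 24, Week 16 was the patient's only partial response on scheduled scans. If that scan was taken on Days 108-112, it enters none of the four landmark rows. Relative to the 15-week row, a 16-week row adds at least this patient to unconfirmed ORR: 1/26 = 3.8 percentage points (1/25 = 4.0), whatever the number of other responders.

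**Off-schedule scans** can still enter any row. They include repeat imaging for suspected pseudo-progression (7.1.3) and a final assessment at discontinuation (7.2.9). A repeat 28 days after Week 8 falls on Days 80-84, inside the 12- and 15-week limits.

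**The case against.** The best case for the SAP has five parts.

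- **The change is permitted.** Protocol 10.1 lets the SAP modify methods and requires an amendment only for major changes to the primary endpoint or its analysis; Part A response is exploratory (SAP 2.6.3). This stands, so no amendment was needed. But permission neither makes the landmarks fit the Part A scans nor explains the omission from section 6.
- **Little is lost.** The 9-week row contains the whole Week 8 window and so gives the 8-week result on scheduled scans. SAP 3.4.2.1 also summarises investigator responses at each planned time point, and the week-16 response still counts in overall unconfirmed ORR and appears in the listings. The point about the 8-week result stands in full. The time-point summary is only a partial substitute: its denominator is patients with an assessment at that visit, and it is not a cumulative response rate on the Efficacy Analysis Set.
- **The 6-week row explains itself.** On scheduled scans its BOR is Not Evaluable, with reasons tabulated. That helps a careful reader, but the ORR row still shows 0% with a confidence interval.
- **A Day 56 limit is strict.** Eight weeks after Day 1 can be read as Day 57, which is also Cycle 3 Day 1, and same-day imaging before dosing is allowed. A Day 57 scan counts in the present 9-week row but not by Day 56. This cost is real but small: Day 56 is the end of the Table 7-1 window, and the SAP already uses window ends at Days 43 and 85.
- **The 3.8 points are conditional.** They are. The protocol gives only the study week, not the scan day.

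**Conclusion.** The point holds and is minor. As written, the SAP gives Part A a 6-week row with no scheduled scan and three further rows resting on one scan. It omits the protocol's cumulative 16-week result and does not record the departure. Confidence is high for the mismatch, which rests on calendar arithmetic and explicit labels in Table 7-1.

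The sizes rest on assumptions: scans on schedule; 26 (or 25) patients in the Efficacy Analysis Set; and, for the added responder, that the patient belongs to that set and was scanned on Days 108-112.

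Overall BOR and ORR, the Not Evaluable reasons and the Part B rows are unaffected, and the SAP performs no hypothesis test (3.1.5). Only the reading of the Part A landmark rows changes.

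**What to change.** 1. In SAP 3.4.1.1, 3.4.1.2, 3.4.2.1 and 3.4.2.2, give Part A two landmarks in place of the four: by 8 weeks (through Day 56) and by 16 weeks (through Day 112). Each row then adds one scheduled scan.
2. Restrict the Week 6 and Week 12 landmarks and their windows to Parts A-2 and B. Leave the Part B rows as they are.
3. Reconcile Part A-2 between the protocol Synopsis (6 and 12 weeks) and 10.6.2 (8 and 16 weeks), noting that Table 7-1 schedules its scans at Weeks 6 and 12.
4. Add a section 6 entry stating the landmarks used for each part and any that differ from the protocol.

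The cost is SAP wording, one section 6 entry and re-programming of the Part A landmark flags. No new data or table is needed. A Part A scan on Day 57 would not count by 8 weeks, but would count by 16 weeks and overall.
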